[name]. JR Carlson Laboratories will manufacture soft gel capsules containing 4000 IU of vitamin D_3 for the intervention arm of the study. JR Carlson Laboratories will also manufacture placebo capsules to be used in the control arm of the study. The study medications will be shipped to the pharmacy of the Ralph H. Johnson VA Medical Center and the Pl's office (for the MUSC site) in Charleston, where it will be stored and dispensed according to the randomization schema developed by the biostatistician.

A multivitamin containing the Institute of Medicine (IOM) recommended cholecalciferol supplementation of 400 IU daily will be provided for all subjects.

4) Procedures and Study Calendar: At Visit #1 (Screening Visit), past medical history, concomitant medications/supplements and inclusion/exclusion criteria will be reviewed and verified. Blood (45mL) will be drawn for Safety labs [Basic Metabolic Panel (BMP), including serum levels of calcium and creatinine; phosphorus, albumin; and Complete Blood Count (CBC) 1, plus serum levels of PSA; cholecalciferol, 25(OH)D, 1,25(OH)D, biomarkers and parathyroid hormone (PTH), all measured as described (68). Allostatic load parameters: serum (HDL, total cholesterol, HbA1c and DHEA-S) and waist/hip ratio and blood pressure measurements will be collected. Urine for calcium/creatinine ratio will also be collected as a safety lab. Five ml of urine, if available, will be collected for biomarkers. A survey will be completed by the subject concerning his decision making about his prostate biopsy. At Visit #2 (Enrollment Visit) baseline lab results, inclusion/exclusion criteria and concomitant medications and supplements will be reviewed. If the subject qualifies for enrollment, he will be randomized, stratified by baseline 25(OH)D level, to one of the two study arms. All subjects will receive a blinded study medication bottle with 130 soft gel capsules (sufficient for 16 weeks of supplementation/placebo before the next scheduled visit) and a supply of a daily multivitamin. They will be instructed to: a) take one soft gel per day for the duration of the study (at least one year); b) return the study medication bottle at the next study visit (after 16 weeks); c) make a notation and report any missed days taking the study medication; d) notify the CRC as soon as possible if the study medication supply is damaged or lost; and e) take the multivitamin daily.

Subsequent visits will be scheduled every 16 weeks. During these visits, bloodwork will be performed for the same tests as at baseline, except for cholecalciferol, 1,25(OH)₂D, HDL, total cholesterol, HbA1C, DHEA-S and PTH. Urine for calcium/creatinine ratio and biomarkers will be collected. The waist/hip ratio and survey will not be completed. Concomitant medications and supplements will be reviewed as will any reports of adverse events. The CRC will collect the returned study medication bottle, assess compliance (pill count), and dispense a new study medication bottle. At the appropriate time (12-18 months from the previous biopsy and/or study enrollment) a Urology Clinic visit will be scheduled for repeat prostate biopsy as per standard of care for active surveillance. After the outcome of the repeat biopsy has been established and each subject has been classified as stable, improving, or progressing, the final visit will be scheduled, (ideally within 16 weeks of the previous study visit). At the final visit: a) bloodwork will be performed for the same tests as baseline, including cholecalciferol, 1,25(OH)₂D, HDL, total cholesterol, HbA1C, DHEA-S and PTH; b) a urine sample will be collected ;c) concomitant medications/supplements will be reviewed; d) reports of adverse events will be reviewed; and e) study medication bottle will be returned and assessed for compliance (pill count), f) the survey concerning the subjects' decision making about his second prostate biopsy will be completed, and q) waist/hip ratio and blood pressure will be measured. Each subject's response will be assessed by the Clinical Co-Investigator based on the repeat biopsy outcome. The outcome, whether stable disease, improvement or progression, will then be discussed with the subject at study exit, in order to determine whether to continue with Active Surveillance or plan additional treatment (hormone therapy. surgery, or radiation therapy).

For the purpose of safety data monitoring, this proposed clinical trial will be under the purview of the Medical/Surgical Data Monitoring Committee at the Hines VAMC (Hines, IL), currently chaired by [name].

Study Visit Flowchart

			lowchart			
	Visit 1	Visit 2	Visit 3	Visit 4 Visit 5	Repeat Biopsy ⁶	Visit 6 Study Exit
Phase	Screening	Enrollment	Treatment	Treatment	Treatment	Exit
Time frame	-1 to -14 days	0 Baseline	+16 weeks	+every 16 weeks (+32,+48)	Urology Clinic schedule	within 16 weeks of previous study visit
(Visit Window)			+ 14 days	+ 14 days		+ 14 days
Informed Consent	X					
BP/HR	Х		Х	Х		Х
Past Medical History	Х					
Inclusion/exclusion criteria	Х	X				
Randomization		Х				
Labwork:						
*BMP ¹ , *phosphorus, * albumin *CBC ²	Х		Х	Х		Х
PSA ³	X		Х	Х		Х
25(OH)D ⁴ and biomarkers	Х		Х	Х		Х
Cholecalciferol, 1,25(OH) ₂ D, PTH ⁵	Х					Х
HDL, total Cholesterol, HbA1C and DHEA-S	Х					Х
*Urine calcium/creatinine ratio	Х		Х	Х		Х
Urine biomarkers	Х		Х	Х		Х
Study VIsit Procedures:						
Prostate Biopsy Survey	Х					Х
Waist/hip ratio	Х					Х
Concomitant meds	Х	Х	Х	Х		Х
Adverse Event Review		Х	Х	X		X
Collect study medication			Х	X		X
Medication compliance						
Dispense study medication		Х	Х	Х		
Dispense Multivitamin		Х				
Follow-up:						
Assessment of repeat biopsy						X
outcome and determination to						
continue active surveillance vs. definitive treatment						

*Safety lab to monitor hypercalcemia; ¹BMP= Basic Metabolic Panel (Ca, Creat, BUN, glucose, Na, K, CO₂); ²CBC=Complete Blood Count; ³PSA= Prostate Specific Antigen; ⁴25(OH)D=circulating vitamin D (calcidiol); ⁵PTH=parathyroid hormone; ⁶Repeat prostate biopsy: to be scheduled by subject and Urologist 12-18 months after previous biopsy, as per Standard of Care/Active Surveillance recommendations.

Expression of VDR (C-20 rabbit polyclonal, Santa Cruz biotechnology), p21 (CP74 monoclonal antibody, SIGMA), TGF β (HPA027923 rabbit polyclonal, SIGMA), COX-2 (H-62, rabbit polyclonal, Santa Cruz biotechnology) will be measured by immunohistochemistry on de-identified sections of pre- and post-study biopsy specimens of enrolled subjects. De-identified paraffin sections of pre- and post-study prostate tissue biopsy specimens will be deparaffinized by serial treatment with xylene, decreasing concentrations of ethanol followed by rehydration with distilled water. Sections will then be pretreated with 0.1% Triton-X100-TBS buffer for 5 min and incubated in 3% H_2O_2 -TBS buffer for 30 min at room temperature to eliminate endogenous peroxidase activity. Following 1hr blocking with 5.0% serum (horse or goat), the sections will be incubated overnight with primary antibodies. The next day, sections will be washed three times (5min/wash) with 0.1% Triton-X100/TBS buffer to remove excess primary antibody. Thereafter, primary antibodies will be detected using HRP-conjugated mouse or rat IgG VECTASTAIN ABC kit and DAB/substrate reagents (Burlingame, CA) according to the manufacturer's instructions. Assessment of the intensity of the immunohistochemical staining (from negative to 4+) will be performed by the

collaborating Pathologist, [name], who will be blinded to the randomization. It must be noted that only core biopsies containing tumor tissue (positive cores) can be informative, and that the paucity of tissue in each core biopsy may allow the testing of a limited number of biomarkers. It is also possible that all biopsy specimens from a particular subject will be needed for diagnostic purposes, and none will be available for research purposes. In any case, we will make every effort to measure the expression of as many relevant biomarkers as the availability of biopsy tissue specimens will allow.

Lab results, when feasible, will be reviewed by a member of the research team within 24 hours.

Abnormal lab results will be reported to the PI and to the Clinical Co-Investigator within 72 hours (allowance for final results and communication over weekends). Critical lab values will be reported to the Clinical Investigator(s) immediately. Subjects and their Primary Care Provider will be notified of any unusual lab results for follow-up as determined by the Clinical Co-Investigator. Laboratory testing will be repeated if necessary. If a subject's serum calcium exceeds 10.5 mg/dl, confirmed via a second test,

the patient will be removed from the study, his Primary Care Provider notified and a follow-up appointment scheduled.

The CRC, PI and Co-Investigators will update and maintain the Regulatory Documents: protocol and amendments, personnel CV's, licenses and training, IRB, VA R&D and FDA correspondence; review and document the safety and research laboratory results; document the study medication receipt, dispensing, return and subject compliance; and maintain subject confidentiality with an assigned de-

identified number for source documents and electronic data entry.

5. Measurement of Primary Outcome: Assessment of tissue biopsy specimens will be performed as part of the standard of care for each subject by the VAMC and MUSC Pathologist, (who will be blinded to the randomization), according to the criteria listed in Table 1.

TABLE 1: DEFINITION OF RESPONSE (R), STABLE DISEASE (SD) AND PROGRESSION (P) OF PATHOLOGY BASED ON CHANGE IN GLEASON SCORE AND NUMBER OF POSITIVE CORES (OUT OF 12) AT BASELINE AND REPEAT BIOPSY.

		GLEASON SCORE		
		LOWER	SAME	HIGHER
Number of Positive Cores	Lower	R	R	Р
	SAME	R	SD	Р
	HIGHER	Р	Р	Р

Assessment of definitive treatment after repeat biopsy and final study visit will be performed by following subjects who return to their Urology clinic for standard of care visits. Serum levels of vitamin D_3 (cholecalciferol) will be determined by high-performance liquid chromatography (HPLC); 25(OH)D, $1,25(OH)_2D$, and parathyroid hormone (PTH) will be determined by radioimmunoassay (RIA), as previously described (38, 68). Serum levels of PSA will be measured in the VAMC Clinical Laboratories. Expression of VDR, p21, TGF β , COX-2, and NF κ B will be measured by immunohistochemistry on sections of pre- and post-study biopsy specimens of enrolled subjects. [name], Professor of Pathology and a Consultant for this study, will be responsible for determining the intensity of immunostaining on de-identified prostate biopsy sections from subjects enrolled in the study. Assessment of the intensity of the immunohistochemical staining (from negative to 4+) will be performed by the collaborating Pathologist, [name], who oversees Pathology Residents rotating through the Pathology Services of the Ralph H. Johnson VA Medical Center and MUSC and will be blinded to the supplementation status of the subjects enrolled in the study.

6. Statistical Considerations

a) Analysis Plan: The first aim of this proposal is to determine whether vitamin D₃ supplementation, compared to placebo, is more effective in maintaining stable or lowered number of positive cores and Gleason score, assessed by the pathologist as per standard of care. Baseline and end-of-study biopsy will be compared in each patient by calculating the change in number of positive cores and the change in Gleason score. These will be described using summary statistics of the ordinal changes and graphical displays. Each patient will also be categorized using three binary indicators: (1) stable Gleason (better or the same score as baseline) vs. worse Gleason (higher Gleason score); (2) stable number of cores (fewer or the same number of positive cores) vs. higher number of cores (more positive cores than at baseline; (3) stable pathology, as defined in Table 1. In each arm of the study and for each outcome, the proportions will be estimated with 95% confidence intervals. Arms will be compared using Fisher's exact test with a 1-sided alpha of 0.05. We will focus on stable number of cores and stable pathology as we expect that there will be less significant changes in Gleason scores. The second aim focuses on additional treatment after the end-of-study biopsy. We will estimate the proportion of men in each group who go on to hormone therapy, prostatectomy, or radiation therapy along with their 95% confidence intervals. We will also compare the proportions across groups using a Fisher's exact test with 2-sided alpha of 0.05.

For aim 3, serum levels of PSA and 25(OH)D will be measured at baseline and every 16 weeks until the end of the study; cholecalciferol, 1,25(OH)₂D, and PTH will be measured at baseline and at the end of the study. Graphical displays will be created to show the trends by patient over time in each group. Linear longitudinal modeling will be used to estimate trajectories over time in each group and to estimate changes from baseline to each relevant time point. Slopes will be estimated and tested for differences from zero in each group. We also plan to compare slopes across groups. Associations between changes in each of these levels with changes in Gleason, number of positive cores, and need for definitive surgery will be estimated using logistic regression models (with pathology outcomes defined above as the outcome measures).

For aim 4, the expression of VDR, CYP27B1, p21, TGFβ, COX-2, and NFκB will be assessed by immunohistochemistry in pre- and post-treatment biopsy tissue specimens. As stated above, assessment of the intensity of the immunohistochemical staining (from negative to 4+) will be performed by the collaborating Pathologist, [name], who will be blinded to the randomization.

b) Sample Size Justification: The sample size was determined based on the ability to detect significant differences in the proportion of subjects with stable number of cores and stable pathology outcomes. Our assumptions regarding null and alternative hypothesis are based on our preliminary data from our single arm study of men receiving an intervention of vitamin D₃ alone with very similar inclusion/exclusion criteria. Our null hypothesis is that both arms will have 40% of men with stable number of cores, and our alternative is that the vitamin D₃ arm will have 70% of men with stable cores (and 40% in the placebo arm). Using a 2-sided alpha of 0.05, we have 87% power to detect this difference with 58 men per arm. Based on our preliminary data there are relatively few men who have an increase in Gleason without an increase in the number of positive cores, so we use the same sample size calculation to power the comparison of proportions of number of men with stable pathology. Examining trends in historical data and our previous study, we would expect 15% of men in the treatment arm to have additional treatment after repeat biopsy, compared to 40% in the placebo arm. This difference can be detected with 81% power - alpha of 0.05. From our earlier studies, we anticipate that some patients will drop out of the study, making them inevaluable for the primary endpoints which require end-of-study biopsy results. As such, we will enroll 68 patients per arm to ensure at least 58 evaluable patients per arm (i.e, allowing 15% dropout). This is a conservative estimate but consistent with previous experience. Aims 3 and 4 are secondary and, as such, power is not provided. Hypothesis testing across groups is not planned for these aims.

Concluding Remarks: The focus of this clinical trial is to test a therapeutic modality that is non-toxic and, therefore, ideal for men with early-stage prostate cancer, who select active surveillance as a treatment option. Furthermore, the randomized clinical trial design will allow us to confirm the beneficial effects of vitamin D₃ supplementation, as we anticipate that the number of subjects showing improvement in the intervention arm will be significantly higher than in the control arm of the trial. One of the overarching challenges in managing early-stage prostate cancer is the ability to distinguish between lethal and indolent disease. Based on the results of our preliminary studies, we anticipate that subjects who respond to our proposed supplementation regimen have indolent disease, while subjects who progress, are affected by aggressive disease that may evolve to invasive and metastatic prostate cancer. Vitamin D₃ supplementation may not only provide a significant addition to active surveillance, but also help us avoid the overtreatment of low-risk disease in subjects who respond to an intervention strategy that is extremely cost-effective and easy to implement. At the same time, this non-toxic regimen would help us identify those patients (non-responders) who are affected by potentially aggressive disease and should consider definitive treatment. Implementation of our proposed randomized clinical trial will provide us with definitive information that would have a major impact towards better management of low-risk disease, while also reducing or eliminating the risk of overtreating indolent prostate cancer...

E. PROTECTION OF HUMAN SUBJECTS

1. Risk to Subjects

- a. Human Subjects Involvement and Characteristics:
 - 1) Characteristics of Subject Population
 - 136 subjects (68 intervention group vs. 68 control group)
 - Males
 - 19 90 years of age
 - Diagnosis of low-grade prostate cancer (biopsy <12 months before screening)
 - Decision to manage prostate cancer with Active Surveillance

2) Inclusion Criteria

- Male 19 90 years old
- Low-grade prostate cancer
- Clinical Stage T1C or T2a
- Serum PSA ≤ 10.0 ng/ml
- Gleason Score ≤ 6 (either architectural pattern ≤ 3)
- Decision to manage prostate cancer with Active Surveillance
- Serum creatinine < 2.0 mg/dL
- Serum phosphorus > 2.3 and < 4.8 mg/dL
- Serum calcium > 8.5 and < 10.5 mg/dL
- Must be capable of giving consent to participate in the study

3) Exclusion Criteria

- Any concurrent malignancy, except non-melanoma skin cancer
- · History of sarcoidosis
- · History of hypercalcemia
- Vitamin D supplementation > 2,000 IU daily
- Primary Hyperparathyroidism (serum Ca > 10.5 mg/dL and PTH > 72 pg/ml)
- Lithium medication

Targeted/Planned Enrollment: 136 Subjects

Ethnic Category	Females	Males	Total
Hispanic or Latino	0	8	8
Not Hispanic or Latino	0	128	128
Ethnic Category: Total of All Subjects	0	136	136

Racial Categories	Females	Males	Total
American Indian/Alaska Native	0	0	0
Asian	0	2	2
Native Hawaiian or Other Pacific Islander	0	2	2
Black or African American	0	50	50
White	0	82	82
Racial Categories: Total of All Subjects	0	136	136

b. Sources of Material

- 1) Research material obtained from living human subjects:
 - Specimens: blood and urine at study visits #1, #3, and subsequent visits (every 16 weeks) until the exit visit; prostate tissue specimens (paraffin blocks) from pre-study biopsy and repeat biopsy prior to study exit.
 - Records: date of birth; race; pre-study prostate biopsy results (Gleason score; number of
 positive cores and percent involvement of positive cores); Progress Note from Urologist
 verifying patient's decision to be on active surveillance; pre-study PSA (prostate specific
 antigen) levels; serum calcium levels; past medical history (inclusion/exclusion criteria).
 - Data: vitamin D levels; safety lab; PSA, HDL, total cholesterol, HbA1C, DHEA-S and PTH results; waist/hip ratio and Blood pressure measurements; decision making about prostate biopsy survey results; post-study pathology results (Gleason score, number of positive cores and percent involvement of positive cores); definitive prostate cancer treatment (including Active Surveillance) following repeat prostate biopsy; specimen biomarkers (blood, urine or prostate tissue).

2) Linkages to Subjects

- Name and SSN [(last 4 digits) at VAMC] or Medical Record Number [(MRN) at MUSC] to identify laboratory specimens and results as per policy and to review medical records
- The Clinical Research Coordinator (CRC) will maintain a Master Enrollment Log which will
 include name, SSN (at VAMC) or MRN (at MUSC), date of birth, address, and telephone
 number with the corresponding de-identified number assigned to each subject. This will be a
 singular list accessed only by the CRC and maintained in secured electronic files on the
 assigned office computer.
- All data collected for analysis will be with the assigned de-identified number.
- The Investigators and CRC will have access to subject identities while performing their study visit procedures
- 3) Collection of specimens, records and data
 - All data will be collected for the specific purpose of this research project

c. Potential Risks

- The risk from drawing blood (venipuncture) include temporary discomfort (likely side effect), bruising (less likely side effect), and infection (rare side effect). Fainting may also occur (rare side effect).
- 2) Loss of Confidentiality of protected health information (unlikely side effect).
- 3) Vitamin D₃ intake of 4,000 I.U. daily (very rare side effects: hypercalcemia, flank pain due to kidney stones, constipation, muscular twitches).
- 4) Alternative treatment is not to participate in the study and continue with an Active Surveillance regimen.

2. Adequacy of Protection Against Risks

a. Recruitment and Informed Consent

- 1) Informed consent document (ICD) will be reviewed and approved by the MUSC IRB IRB of record for the Ralph H. Johnson VAMC. No children will be involved in this study.
- 2) Eligible subjects will be recruited by [name], Chief of Urology at the Charleston VAMC and Professor of Urology at MUSC, and [name], Professor of Radiation Oncology at MUSC and enrolled into the study by the CRCs.
- 3) All research personnel have successfully completed all research compliance requirements for human studies and for obtaining informed consent from eligible subjects.

- 4) After [name] or [name] has explained the general purpose of the study to an eligible subject and the potential subject states he will consider participating in the study, the CRC will meet the subject, and review the background, purpose, procedures and objectives of the study. Adequate time will be given to the subject for reading the ICD and the Health Insurance Portability and Accountability Act (HIPAA) document, discuss the documents with his significant other(s), ask questions and then determine if he wishes to participate in the study. Only when the subject states that he wishes to participate, will the ICD and the HIPAA be signed.
- 5) If a potential subject calls the CRC after receiving a verbal referral or letter from [name] or [name], the background, purpose, procedures and objectives of the study will be reviewed with him. If the subject states he wishes to participate, a copy of the ICD will be mailed to the subject to be read thoroughly and discussed with family members before his initial visit. At his first visit, the ICD will be reviewed, and questions encouraged and answered before the ICD is signed. Time for the subject to read the HIPAA and ask questions will be allotted before it is signed. The ICD/HIPAA will be signed only after the subject states he wishes to participate and before any study procedures are initiated.
- 6) Only subjects who are capable of giving consent may enroll in the study.
- 7) All aspects of the recruiting and consent process will be documented in Progress Notes maintained as part of the subject's Source Documents.

b. Protection Against Risk

- Venipuncture: Risk will be minimized by having licensed nursing personnel perform the
 procedure using hospital-approved techniques to minimize hematoma, infection and/or
 discomfort. Subjects will be sitting for the procedure and asked whether they feel dizzy before
 allowed to stand after their blood sample has been collected.
- 2) Loss of Confidentiality of protected health information
 - Data will be collected and maintained according to VAMC and MUSC guidelines.
 - Subjects will be de-identified with an assigned number that will not be related to any personal information.
 - The original signed ICD and HIPAA with subject signature/name will be filed in a locked cabinet and kept separate from the source documents maintained for each subject.
 - Source documents will be de-identified and will be transported and/or handled only by the CRC, during a scheduled study visit. At all other times, these documents will be stored in a locked cabinet.
 - Only the Master Subject List will contain subject identified information. It will be maintained in a secured file server that is accessed only by the CRC through the assigned office computer.
 - A database will be designed for each component of data collection. There will be no patient identifiable information on the outcome databases; linkage can be accomplished only by the unique de-identification code.
 - Electronic data will be maintained in the secured file server, not on an individual computer hard drive or laptop. The specific study files are limited to the CRC, Co-Investigators and the PI
 - No names or identifying information will be used in any presentations and/or publications.
- 3) Vitamin D₃ intake of 4000 IU daily: the study drug dose is the safe upper limit according to the Institute of Medicine (IOM) report released in December 2010. The vitamin D₃ supplement will be purchased through JR Carlson Laboratories, Inc. This company is based and manufactures its products in the United States. It has provided the vitamin D₃ supplement for multiple studies at MUSC, involving hundreds of subjects, with no related adverse events.
- 4) This is a double-blind placebo controlled study, therefore to correct potential insufficient levels of circulating vitamin D₃ for those subjects who are assigned to the placebo group, all subjects will receive a daily multivitamin containing the IOM recommendation of cholecalciferol supplementation.

- 5) Subjects will have routine safety blood and urine tests at every clinic visit except #2 (enrollment). Lab results, when feasible, will be reviewed by a member of the research team within 24 hours. Abnormal lab results will be reported to the Clinical Investigator within 72 hours (allowance for final results and communication over weekends). Critical lab values will be reported to the Clinical Investigator(s) immediately. Subjects and their Primary Care Provider will be notified of any unusual lab results for follow-up as determined by the Clinical Investigator. Laboratory testing will be repeated if necessary.

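### Aim 4 staining: the only detection reagent named is for mouse or rat IgG, yet three of the four listed primary antibodies are rabbit

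*Combined protocol and SAP*

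**What the plan says.** The staining method stands in Section D.4 (Procedures and Study Calendar), in the paragraph after the visit flowchart. It names four primary antibodies:

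- VDR: "C-20 rabbit polyclonal, Santa Cruz biotechnology"
- p21: "CP74 monoclonal antibody, SIGMA"
- TGFβ: "HPA027923 rabbit polyclonal, SIGMA"
- COX-2: "H-62, rabbit polyclonal, Santa Cruz biotechnology"

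Sections are blocked with horse or goat serum, incubated overnight with the primaries and washed. Then "primary antibodies will be detected using HRP-conjugated mouse or rat IgG VECTASTAIN ABC kit and DAB/substrate reagents", following the kit maker's directions. A pathologist blinded to randomization grades intensity from negative to 4+. The paragraph also warns that each core yields little tissue, that only some biomarkers may be testable, and that some subjects may have no tissue for research.

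The analysis plan in Section D.6(a) is wider than the list of primaries: "the expression of VDR, CYP27B1, p21, TGFβ, COX-2, and NFκB will be assessed by immunohistochemistry". Section D.6(b) makes Aim 4 secondary, gives no power for it and plans no hypothesis test between groups.

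**The concern.** In indirect staining the detection reagent has to recognise the species in which the primary antibody was raised. A laboratory that ordered exactly what Section D.4 names would have no reagent stated to recognise rabbit antibody, although rabbit is the only host the paragraph states for any primary.

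What is at stake is how the Aim 4 readout would be interpreted. If a rabbit primary were poorly detected, the pre- and post-study sections could both grade low, and the pair could be read as no change when the assay had not worked. Section D.4 asks for no positive-control section, no no-primary control and no cross-reactivity check, so nothing in the written procedure requires such a failure to be found before grading. Because tissue is scarce by the plan's own account, repeating a run may not always be possible.

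**Working it through.** No figure in the plan depends on this point, so the check is a comparison of texts and a count.

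**Inputs.** Hosts and detection species come from the staining paragraph of Section D.4. Marker lists come from Section A (Aim 4) and Sections D.4, D.5 and D.6(a).

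**Step 1: host of each primary against the named detection species.** The kit phrase is read in its natural sense, as a kit that detects mouse or rat IgG.

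| Aim 4 marker | Primary in D.4 | Host as stated | Host among mouse or rat? | Host among mouse or rabbit, if rat is a slip? |
|---|---|---|---|---|
| VDR | yes | rabbit | no | yes |
| TGFβ | yes | rabbit | no | yes |
| COX-2 | yes | rabbit | no | yes |
| p21 | yes | not stated | cannot be determined | cannot be determined |
| CYP27B1 | none | – | – | – |
| NFκB | none | – | – | – |

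**Step 2: counts under the text as written.**

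- Listed primaries not matched: 3 of 4 = 75%.
- Aim 4 markers not matched: 3 of 6 = 50%.
- Full tally: 3 not matched + 1 undetermined + 2 with no primary named = 6.

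**Step 3: does other text supply the missing reagent?** No rabbit-directed detection reagent is named elsewhere in the document. The reference to the manufacturer's directions governs how the named kit is used, not which kit is chosen.

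**Step 4: the marker lists side by side.**

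| Section | Markers | Count |
|---|---|---|
| A, Aim 4 | VDR, CYP27B1, p21, TGFβ, COX-2, NFκB | 6 |
| D.4, primaries named | VDR, p21, TGFβ, COX-2 | 4 |
| D.5 | VDR, p21, TGFβ, COX-2, NFκB | 5 |
| D.6(a) | VDR, CYP27B1, p21, TGFβ, COX-2, NFκB | 6 |

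CYP27B1 is missing from D.4 and D.5, and NFκB is missing from D.4. This is a separate inconsistency and says nothing about detection species.

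**The case against.** The best answer is that this is one wrong word. No listed primary is stated to be rat and three are rabbit, so rat could easily have been typed for rabbit. The two alternative blocking sera would fit the use of two different secondary antibodies. The kit phrase is itself loose: it does not say anti-mouse or anti-rat. On this view the laboratory would have used suitable reagents whatever the text says, and an experienced pathologist would notice a marker that failed throughout.

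Much of this stands as explanation. A slip is plausible, and a uniform failure might well be noticed at grading. But the document does not confirm the slip, and this is the operative assay text that staff would follow. If it is a slip, the text still needs the correction.

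It is also fair to say that the plan undertakes to measure only as many markers as tissue allows. That softens the commitment to six markers, but it does not explain why two of them have no primary named.

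A reader might go further and infer that VDR, TGFβ and COX-2 would give no valid specific signal. The document does not support that. The result depends on the secondary antibody actually supplied and on its cross-reactivity, and neither is given. A reader might also infer that p21 alone of the six has a working antibody chain. That is not supported either, because the host of the p21 antibody is not stated.

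**Conclusion.** The inconsistency is real and can be seen within one paragraph. The named detection species covers none of the three primaries described as rabbit, which is half of the six Aim 4 markers, and the match for p21 is unknown. The supportable conclusion is that a valid signal for VDR, TGFβ and COX-2 is not assured by the procedure as written. It is not that the assays would fail.

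This rests on two assumptions: that the kit phrase identifies the species to be detected, and that no unstated cross-reactivity or substitute reagent fills the gap.

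The reach is limited. Aim 4 is secondary and unpowered and has no planned between-group test. The primary outcome (Gleason score and positive cores), the sample size and the other aims do not depend on this staining. The correction should be made because it is cheap and the tissue is scarce, not because the trial's main conclusion is at risk.

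**What to change.** Before Aim 4 staining starts, amend the staining paragraph of Section D.4:

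1. State the host species of every primary, including p21.
2. Replace the single mouse-or-rat phrase with detection matched to each host: a rabbit IgG kit for VDR, TGFβ and COX-2, and for p21 the kit that matches its host once stated.
3. Grade only runs in which a positive-control section stains and a no-primary control does not.

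As a separate edit, make the marker lists in Section A, D.4, D.5 and D.6(a) agree. Either name primaries for CYP27B1 and NFκB in D.4 and add CYP27B1 to D.5, or remove the markers that will not be stained from the aim and the analysis plan.

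The cost is protocol wording, matched reagents and a few control sections. No extra patient biopsies are needed. Because research tissue is limited, the amendment should say where the control sections will come from. Adding the two missing primaries, if that option is taken, would also use further sections.
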